6.1.1 Adverse Event Lists(s) for Idelalisib

Symptomatic adverse events are infrequent, usually low-grade, and not clearly idelalisib-related. Among Grade ≥ 3 nonhematological adverse events occurring in $\geq 5\%$ of patients, pneumonia was observed most frequently, occurring in 24% of patients with CLL. In most instances, these cases were considered bacterial in origin, based either on culture results or on response to conventional antibiotics; 2 patients with CLL have had pneumocystis pneumonia. The observed rate of pneumonia of any type in patients with CLL receiving idelalisib over 360 patient-months of observation has been 0.04 pneumonias/patient/month; this rate is modestly less than the rate of 0.06 pneumonias/patient/month reported in the literature for a comparable population of CLL patients [9]. There have however also been a few cases of what appears to be a steroid-responsive idelalisib-related pneumonitis. Other nonhematological adverse events in patients with CLL have included diarrhea (4%), and fatigue (4%). Grade ≥ 3 hematological laboratory abnormalities include neutropenia (8%), thrombocytopenia (4%), anemia (2%) and neutropenic fever (7%).

6.1.2 Adverse Event List(s) for Ofatumumab

The primary adverse event associated with ofatumumab is infusion reactions during drug administration. The management of those is discussed under drug administration. Other potential concerns include LFT abnormalities, hepatitis B reactivation, and PML, which has been observed with another CD20 antibody, rituximab.

6.2 Toxicity Management

Patients should be followed closely for adverse events or laboratory abnormalities that might indicate idelalisib or ofatumumab-related toxicity. Recommendations for idelalisib dose modification and when to hold and restart drug are provided below. If a patient experiences a idelalisib-related adverse event requiring dose modification during the course of idelalisib therapy, then study drug administration should be held, as necessary, until the adverse event resolves or stabilizes to an acceptable degree. Thereafter, idelalisib may be reinstated, but the

CONFIDENTIAL

This document is confidential. Do not disclose or use except as authorized.

dose of idelalisib should be reduced by 1 dose level (except for hematologic toxicity or grade 3 infections or grade 3 asymptomatic laboratory abnormalities, when dose may potentially be maintained at the investigator's discretion); dose adjustments may be made. If the patient cannot tolerate idelalisib at Dose Level -1 (100 mg/dose BID) then the patient should be discontinued from study drug therapy.

After a dose is reduced, the dose need not be re-escalated, even if there is minimal or no toxicity with the reduced dose. However, if the patient tolerates a reduced dose of idelalisib for ≥ 4 weeks then the idelalisib dose may be increased to the next higher dose level, at the discretion of the investigator. Such re-escalation may be particularly warranted if further evaluation reveals that the adverse event that led to the dose reduction was not study drug-related. Successive adjustments to progressively higher dose levels can be made at 4-week intervals. The starting dose level (150 mg BID) should not be exceeded.

Except as specified below for hematologic and liver toxicity, in most cases of adverse events both study drugs will be held until resolution.

Table 5

Dose Level	Idelalisib Dose
-1	100 mg BID (1 tablet, 100 mg)
0	150 mg BID (1 tablet, 150 mg)

Management of Hepatic Adverse Events in Patients on or soon after discontinuation of Idelalisib

If at any point either AST or ALT reaches grade 2 elevation or higher on any test, idelalisib will be held and prednisone will either be started or increased to 1 mg/kg daily, rounded up to the nearest multiple of 10 mg. If direct or total bilirubin is elevated (grade 2 or higher) and not due to an obvious unrelated cause such as hemolysis or gilbert's syndrome, drug should be held. Monitoring will continue twice weekly until LFTs trend towards normalizing, at which point labs may switch to once weekly, based on conversation between the treating investigator and the overall PI. The labs on non-protocol specified treatment days may be obtained locally at the discretion of the site-responsible investigator but must be followed up the same day by the study site. For patients with a grade 2-3 transaminitis, following resolution of AST or ALT to normal (grade 0), consideration may be given to resuming idelalisib at a one dose level reduction, at 100 mg BID. Steroid dose should be held at its prior level for at least one week after idelalisib is restarted, following which if AST / ALT remain within normal limits, prednisone may be tapered at a recommended rate of 10 mg per week. LFTs should be checked weekly for at least twelve weeks after resuming study drug, even while on prednisone

Patients whose AST or ALT reach grade 4 but resolve rapidly with steroids may be reinitiated on idelalisib while on steroids, as per the above protocol for grade 2-3, at the discretion of the treating investigator in consultation with the PI. Patients whose grade 4 AST or ALT continue to rise despite steroids, or fail to improve in 3-5 days after initiation of steroids, should be discussed with the overall PI, with consideration given to initiation of mycophenolate mofetil 2000 mg BID. These patients will also be carefully assessed for the suitability of reinitiation of idelalisib, in consultation with the overall PI. Otherwise subjects who reinitiate at 100 mg BID with stable normal LFTs and who taper off prednisone may be considered for dose re-escalation to 150 mg BID, after they reach cycle 5 or beyond.

Several subjects have had stable minor grade 1 to low grade 2 AST/ALT elevations typically developing in cycle 3-4. If twice weekly monitoring shows stability at this level, , as either an initial event or a subsequent event, initiation of prednisone and holding idelalisib will be discretionary if LFTs remain less than grade 3, with approval of the overall PI.

Subsequent Events of Transaminitis During Cycle 1-4

If AST / ALT go back up to grade 1, idelalisib and prednisone may be continued at current level or prednisone may be resumed or increased to 40 mg daily at the discretion of the treating investigator and PI, but if they rise to grade 3 or higher, follow above recommendations for grade 2 or above (i.e. hold idelalisib and increase steroids back to 1 mg/kg). Monitoring will continue twice weekly until LFTs trend towards normalizing, at which point labs may switch to once weekly, based on conversation between the treating investigator and the overall PI. These additional labs should be continued at least twelve weeks after resuming study drug. The labs on

CONFIDENTIAL

This document is confidential. Do not disclose or use except as authorized.

non-protocol specified treatment days may be obtained locally at the discretion of the site-responsible investigator.

Alternative management plans for hepatotoxicity may be acceptable with prior approval of the overall PI, except in cases of fulminant grade 3/4 events.

Management of Transaminitis Cycle 5 and onward

Several subjects have had stable minor grade 1 to low grade 2 AST/ALT elevations at this point in the study, as either an initial event or a subsequent event. Therefore initiation of prednisone and holding idelalisib will be discretionary if LFTs remain less than grade 3. On initial observation of this finding, LFTs must be repeated twice per week for at least 2 and up to 4 weeks or an alternative monitoring plan should be discussed with the overall principal investigator. Very slight elevations (approximately 1-5 points) may not necessitate repeat labs in the absence of clinical symptoms. If at any point either AST or ALT reaches grade 3, Idelalisib must be held and LFTs re-checked within 2-3 days; prednisone may be started at the discretion of the treating investigator. If either AST or ALT is greater than 10 times the ULN at any time, or if AST or ALT continue to rise after stopping study drug, then Prednisone must be started at 1mg/kg and LFTs must be checked twice per week until resolution to grade 0, at which time Idelalisib may be resumed. If Idelalisib is resumed prednisone should be continued at current dose for at least one week prior to beginning taper as described above. All subjects will continue with at least weekly LFTs for up to 12 weeks while on stable dose of Idelalisib and off prednisone. If at that time LFTs have remained stable grade 1 or within normal limits, the frequency of LFT checks may decrease to every 2-4 weeks at the discretion of the treating investigator with communication with the overall PI. Some variation in these guidelines may be considered upon consultation of the treating investigator with the overall PI.

Ofatumumab has also been associated with LFT abnormalities. Of particular concern in this context is the possibility of reactivated or new hepatitis. In particular, patients enrolled on study who had HBcAb positive with HBsAg negative may be at (low) risk for reactivation. For that reason, those patients were screened prior to enrollment for HBV DNA and required to be negative. If such a patient develops any even grade 1 LFT elevation, HBV DNA must be performed at the time of this occurrence, in addition to the already planned every 2 month HBV DNA PCR testing from the start of treatment throughout the treatment course. Monitoring during the on treatment periods is required at least every 2 months and during follow-up at a minimum of every 2-3 months up to 12 months after the last dose. If the subjects' HBV DNA becomes positive during the study, the investigator should manage the clinical situation as per the standard of care of that institution, likely including holding drug and instituting antiviral therapy. Also, if a subject's HBV DNA becomes positive during the study, notify Novartis (contact information located in 11.4.1). The risks and benefits of continuing or discontinuing ofatumumab should be discussed with the overall PI before treatment decisions are made for that individual subject. Subjects initiated on antiviral therapy who achieve suppression of their HBV DNA viral load may be eligible to continue on the study at the discretion of the treating investigator and the overall PI.

CONFIDENTIAL

This document is confidential. Do not disclose or use except as authorized.

For those patients with at least grade 2 elevations in ALT/AST and in bilirubin (only if direct), drug should be held as noted above, and they should undergo the further workup below as well as the monitoring discussed above. These patients will have ofatumumab held as well as idelalisib, until resolution. Further workup is particularly warranted in patients who first experience a serum ALT/AST elevation 12 weeks from the start of idelalisib therapy, who have an elevation in serum bilirubin concentration, or who have other characteristics that suggest an atypical change in transaminase values. Further workup may include: obtaining a history of recent symptoms/illnesses and of relevant past history (eg, history of hepatitis or of hepatitis A or hepatitis B vaccination); obtaining information regarding concomitant drug use (prescription and nonprescription medications, dietary supplements, alcohol, illicit drugs, special diets); questioning the patient regarding potential exposure to environmental toxins; ruling out viral hepatitis A, B, C, D (if hepatitis B is positive), and E, Epstein-Barr virus, cytomegalovirus, autoimmune hepatitis, anti-smooth muscle antibody, and Type 1 anti-liver kidney microsomal antibodies, alcoholic hepatitis, nonalcoholic steatohepatitis, hypoxic/ischemic hepatopathy, and biliary tract disease; obtaining additional tests to evaluate liver function (eg, imaging as appropriate, and prothrombin time [PT], activated partial thromboplastin time [aPTT], international normalized ratio [INR], albumin); and considering gastroenterology or hepatology consultation [FDA 2009]

PML

Progressive multifocal leukoencephalopathy (PML) is a viral-induced demyelinating disease of the central nervous system usually occurring in the immunocompromised individual. JC virus infection resulting in PML and death has been reported in rituximab-treated subjects with hematologic malignancies or with systemic lupus erythematosus (SLE), an indication for which rituximab has not been approved. In the literature, PML has been reported to occur in 0.52% of CLL subjects and in approximately 5% of fludarabine-treated B-CLL subjects. One case of PML was reported in a very ill CLL subject treated with ofatumumab, previously treated with alemtuzumab and fludarabine and with very low CD4 cell count.

Investigators and nurses should pay careful attention for signs and symptoms consistent with a diagnosis of PML. Signs and symptoms of PML include visual disturbances, ocular movements, ataxia, and changes in mental status such as disorientation or confusion. These symptoms are not an exhaustive list and the investigator should exercise judgment in deciding to report signs and symptoms to the overall PI and Novartis promptly. Please see Appendix D for a symptom screening questionnaire.

If a subject develops neurological signs or symptoms consistent with PML treatment should be halted and the subject referred to a neurologist for evaluation. The investigator will contact the Novartis within 24 hours of being notified of a participant's potential signs and symptoms of PML. At a minimum, blood JCV PCR and/or MRI will be performed and if either is positive perform Cerebrospinal Fluid (CSF) JCV PCR. If blood JCV PCR and MRI are negative, the investigator will contact the Novartis for appropriate action to be taken. If blood JCV PCR and/or MRI are positive, the subject should proceed to the Follow-Up Period. All such subjects will be followed until resolution. Any subject with a diagnosis of PML will be withdrawn from ofatumumab. There are no known tests that can reliably determine who is at increased risk for

CONFIDENTIAL

This document is confidential. Do not disclose or use except as authorized.

developing PML. There are no known interventions that can reliably prevent PML or adequately treat PML if it occurs.

Hematologic Toxicities

While myelosuppression is not a prominent toxicity of idelalisib in previous experience, dose modification provisions for patients experiencing neutropenia or thrombocytopenia are provided as a precaution. Recommendations for dose modification based on the type and severity of adverse events or laboratory abnormalities are provided below in Table 6. Whenever possible, any dose adjustment of idelalisib should be discussed between the treating investigator and the overall Principal Investigator prior to implementation. Myelosuppression is also not a prominent complication of ofatumumab therapy, although neutropenia can occur. Ofatumumab will generally not be held for myelosuppression, but appropriate growth factor and transfusion support will be employed as needed.

Either or both drugs may be held for up to six weeks for resolution of toxicity without removing a participant from the study. Longer holds are acceptable in the post-induction phase following discussion with the overall principal investigator.

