This study activated for enrollment on June 16, 2014, and since then 15 patients have initiated on therapy. Among the first 8 patients to reach cycle 2, two patients developed grade 4 transaminitis. Transaminitis is a well-known side effect of idelalisib, and included as a black box warning in the FDA approved label. In these two cases the onset was rapid, and continued to increase after discontinuation of the drug. We have therefore previously amended the protocol to significantly increase the frequency of LFT monitoring during the high risk period. Additional observation has shown that this transaminitis appears to be inflammatory, based on the results of two liver biopsies showing a CD8 T cell infiltrate and the response of these patients to steroids and/or mycophenolate mofetil. We have developed an algorithm for the early initiation of steroids with the first signs of transaminitis which together with the frequent monitoring has resulted in predictable safety and much shorter drug interruptions. This amendment served to further refine that treatment algorithm.

An amendment was submitted in January 2015 to add correlative studies, in particular sequencing analysis of the clonal composition of CLL in PB vs BM at baseline, mid treatment and at final restaging. This analysis will still occur.

Rationale for Current Amendment 3/14/16

This amendment will take all patients off idelalisib, but allow them to receive ofatumumab and be followed per protocol assessments. All patients had discontinued idelalisib as of 3/11/16. They will undergo a full disease restaging with correlative samples within 30 days and be followed per protocol until further therapy, and after that just for overall survival.

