5. TREATMENT PLAN

Treatment will be administered on an outpatient basis. Expected toxicities and potential risks as well as dose modifications for ofatumumab are described in Section 6 (Expected Toxicities and Dosing Delays/Dose Modification). No investigational or commercial agents or therapies other than those described below may be administered with the intent to treat the participant's malignancy.

Idelalisib lead-in followed by ofatumumab 8 wks later

All therapy with idelalisib has been discontinued. Patients on drug stopped as of 3/11/16. Those currently receiving ofatumumab may complete the planned course and evaluations as below. Those who have not yet reached day 57 may initiate ofatumumab at present. On day 57, ofatumumab will begin with the 300 mg dose. Ofatumumab will then be administered at 1000 mg weekly to complete 8 weeks (days 64, 71, 78, 85, 92, 99, 106) throughout Cycles 3 and 4. Cycle 4 will last 49 days (7 weeks) to accommodate the Ofatumumab dosing schedule. This will be followed by monthly ofatumumab on weeks 20, 24, 28, 32 to complete 4 additional cycles (5-8). The overall induction treatment period will then be up to 8 months, including whatever idelalisib was received prior to March 11, 2016. Restaging with CT scans will happen after Cycle 2, on cycle 4 day 22, and a final restage will occur 2 months after the completion of ofatumumab. There will be a tumor response assessment done via physical exam after Cycle 8.

Table 1: Treatment Description

Agent	Pre-medications; Precautions	Dose	Route	Schedule	Cycle Length
Idelalisib	None	150 mg BID	Oral	Discontinued	28 days (4 weeks) (Except cycle 4-49 days, 7 weeks)
Ofatumumab	Pre-medication before each ofatumumab infusion must be given within 30 minutes to 2 hours prior to the treatment: Acetaminophen 1000 mg po Benadryl 50 mg IV or po Methylprednisolone 50 mg IV*	300 mg at 0.3 mg/ml in NS; followed one week later by 1000 mg at 1 mg/ml in NS	IV after administration of Idelalisib and premeds	Weekly x 8 doses, then monthly x 4 doses	
* If the 2 nd infusion has been completed without the subject experiencing any grade = 3 AEs, pre-medication with glucocorticoid may be reduced or omitted before the 3 rd to N th infusion at the discretion of the investigator.					

CONFIDENTIAL

This document is confidential. Do not disclose or use except as authorized.

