5.2 Agent Administration

5.2.1 Idelalisib will not be given

5.2.2 Ofatumumab

The dosing of ofatumumab in CLL should consist of an infusion of 300 mg on Day 1, an infusion of 1000 mg weekly for 7 additional doses, and then infusions of 1000 mg monthly for up to 4 doses. The monthly ofatumumab doses should be given on Day 1 of the cycles.

First Infusion of 300 mg Ofatumumab (CLL)

The first dose administered of ofatumumab in CLL should be 300 mg to minimize infusion reactions. The initial rate of the first infusion of 300 mg ofatumumab (0.3 mg/mL) should be 12 mL/h. If no infusion reactions occur the infusion rate should be increased every 30 minutes, to a maximum of 400 mL/h, according to Table 2. If this schedule is followed, the infusion duration will be approximately 4.6 hours. If the ofatumumab dose cannot be completed on day 1 in clinic, the remaining dose may be completed the following day with the same premedications.

Table 2: Infusion rate at 1st ofatumumab infusion (300 mg)

Time	mL/hour
0 – 30 minutes	12
31 – 60 minutes	25
61 – 90 minutes	50
91 – 120 minutes	100
121 - 150 minutes	200
151 - 180 minutes	300
181+ minutes	400

CONFIDENTIAL

This document is confidential. Do not disclose or use except as authorized.

If an infusion reaction develops, the infusion should be temporarily slowed or interrupted. Upon restart, the infusion rate should be half of the infusion rate at the time the infusion was paused. If, however, the infusion rate was 12 mL/hour before the pause, the infusion should be restarted at 12 mL/hour. Thereafter, the infusion rate may be increased according to the judgment of the investigator, in the manner described in this section. If the infusion is not completed on day 1, the remaining infusion may be completed on day 2 at the starting infusion rate used on day 1.

First Infusion of 1000 mg Ofatumumab

The initial rate of the first infusion of 1000 mg ofatumumab (1 mg/mL) should be 12 mL/h. If no infusion reactions occur the infusion rate should be increased every 30 minutes, to a maximum of 400 mL/h, according to Table 3. If this schedule is followed, the infusion duration will be approximately 4.6 hours. If the ofatumumab dose cannot be completed on day 1 in clinic, the remaining dose may be completed the following day with the same premedications.

Table 3: Infusion rate at 1st ofatumumab infusion (1000 mg)

Time	mL/hour
0 – 30 minutes	12
31 – 60 minutes	25
61 – 90 minutes	50
91 – 120 minutes	100
121 - 150 minutes	200

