7. DRUG FORMULATION AND ADMINISTRATION

Table 6. Recommendations for Dose Modification of Study Drug(s) Based on Type and Severity of Adverse Event or Laboratory Abnormality

Non-Hepatic and Non-Hematological Study Drug-Related Event				
CTCAE Grade	Grade 1	Grade 2	Grade 3	Grade 4
Idelalisib and Ofa Dosing Recommendation	Maintain dose level	Maintain dose level	Withhold drugs until toxicity is Grade ≤1. May resume idelalisib only at next lower dose level for most toxicities, but may resume at current dose level in the case of grade 3 infections, grade 3 nausea/vomiting/diarrhea that can be symptomatically managed, grade 3 asymptomatic laboratory abnormalities or grade 3 infusion reactions.	
Hepatic Study Drug-Related Event (Elevation in ALT, AST, or Bilirubin)				
CTCAE Grade	Grade 1	Grade 2	Grade 3	Grade 4
ALT/AST	>ULN-3 x ULN	>3-5 x ULN	>5-20 ULN	>20 x ULN
Bilirubin	>ULN-1.5 x ULN	>1.5-3 x ULN	>3-10 x ULN	>10 x ULN
Idelalisib and Ofa Dosing Recommendation	See Section 6.2: Management of Hepatic Events.			
Hematological Idelalisib -Related Event				
IWCLL Grade	Grade 1	Grade 2	Grade 3	Grade 4
Neutropenia (ANC x 10 ⁹ /μL)	ANC <LLN-1.5	ANC <1.5-1.0	ANC <1.0-0.5	ANC <0.5
Thrombocytopenia (platelets x 10 ⁹ /μL)	Platelets 11-24% below baseline	Platelets 25-49% below baseline	Platelets 50-74% below baseline	Platelets ≥75% below baseline or ≤25K
Idelalisib Dosing Recommendation	Maintain dose level	Maintain dose level	Maintain dose level; support with g-CSF growth factors at investigator discretion	During combination therapy period, consider G-CSF support and maintain current study drug dose level and schedule. During initial and continuing single-agent study drug therapy period, consider G-CSF support and continue study drug at initial or lower dose level at investigator discretion.

***Note: In any case where Idelalisib is held, ofatumumab should also be held. The assessment schedule is also held in cases where study drug is held for greater than half a week.*

Abbreviations: ALP, alkalkine phosphatase; ALT, alanine aminotransferase; ANC, absolute neutrophil count; AST, aspartate aminotransferase; CTCAE, Common Terminology Criteria for Adverse Events; LLN, lower limit of normal; ULN, upper limit of normal

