Study Drug Administration	
Idelalisib Administration Guidelines are found in Section 5.0 through 5.2,1 including Table 1
 
 Dosing will start on Cycle 1, Day 1 Always administered BEFORE Ofatumumab when given on the same day Oral, taken twice per day approximately 12 hours apart. May be taken with or without food; Note: Food consumption should be recorded on PK days – Section 5.2.1 Tablets must be swallowed whole with 100 – 200 mL of water. Participants must be instructed not to bite or chew the tablets. In case of breakage of tablets in the oral cavity, additional water should be taken as a rinse. Missed doses may be taken within 6 hours of the scheduled dosing time. Vomited doses can only be retaken if the tablet is visible in the vomitus. 
Ofatumumab Administration Guidelines are found in Sections 5.0 through 5.1; 5.2.2 and 7.2
 
 Dosing will start on Cycle 3, Day 1 and continue once weekly for 8 weeks (Cycles 3 and 4). This will be followed by monthly dosing for four additional cycles (Cycles 5, 6, 7 and 8) Administered IV through infusion tubing set supplied by Sponsor. Please note that infusion time can be up to 4.6 hours. Do NOT mix with any other meds. IV line must be flushed with NS before and after completion of infusion. Premedication regimen – See Table 1 in Section 5.0 Please review Section 5.2.2 and Tables 2 through 4 for specific instructions on the rate of infusion Infusion reactions are an expected risk – monitor patient closely – Section 6.1.2 Please review 7.2.4 and Figure 1 for detailed instructions on the infusion set up for Ofatumumab, including the use of a 0.2 micron polyether sulfone in-line filter. 
NOTE: Criteria to treat is found in Section 5.1

Dose Mods & Toxicity	
Dose Modifications/Dosing Delay for Toxicity are outlined in Section 6
 
 This protocol uses NCI CTCAE criteria, version 4.0 – Section 6 Participants must be monitored for s/sx consistent with PML and for Hepatic Adverse Events – see Table 6 and Section 6.2 for a description of the signs and symptoms. See also Appendix D for a symptom screening questionnaire. See Section 6.3 and Table 6 for dose modifications and delays.

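### Section 6.2, Table 6 and the nursing page still permit or describe idelalisib dosing after the amendment that stopped it for every patient

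*Combined protocol and SAP*

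**What the plan says.** **Text that stops the drug.** The rationale for the current amendment (Section 2.5, dated 3/14/16) says: "This amendment will take all patients off idelalisib, but allow them to receive ofatumumab and be followed per protocol assessments". It adds that every patient was already off idelalisib by 3/11/16. Section 5 says "All therapy with idelalisib has been discontinued", and Section 5.2.1 consists of one statement: "Idelalisib will not be given". Sections 1.1 and 2.2.4 give the reason, an excess of deaths, mostly from infection, in three other idelalisib trials.

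**Text that still allows or describes dosing.**
- Section 6.2, cycle 5 onward: "LFTs must be checked twice per week until resolution to grade 0, at which time Idelalisib may be resumed".
- Section 6.2, first transaminitis event: restart at a reduced dose after grade 2-3, possible restart after grade 4, and patients who restart and come off prednisone with stable normal tests "may be considered for dose re-escalation to 150 mg BID".
- Table 6, non-hepatic and non-hematological events of grade 3-4: "May resume idelalisib only at next lower dose level for most toxicities", with listed exceptions.
- Table 1, ofatumumab route: "IV after administration of Idelalisib and premeds".
- Nursing page, idelalisib entry: "Always administered BEFORE Ofatumumab when given on the same day", together with timing, swallowing, missed-dose and vomited-dose steps.

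**The concern.** A protocol that withdraws a drug for safety should leave site staff one answer to the question of whether it may be given. Here the answer depends on which page is open. The treatment plan says no. The toxicity rules say yes under conditions, and the nursing page describes how.

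The toxicity section cannot be set aside as obsolete. Its hepatic subsection is headed as applying both to patients on idelalisib and to those who have recently come off it. A site handling a liver enzyme rise after the stop is therefore sent to the subsection that contains the restart permissions. At stake is possible re-exposure to a withdrawn drug. There is also a second ambiguity: whether ofatumumab may continue when idelalisib is not being given.

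**Working it through.** No arithmetic applies, because the point rests on no sample size, rate or error level. The check sets each location against the stop in Sections 2.5, 5 and 5.2.1.

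| Location | What it still does | Conflict with the stop? |
|---|---|---|
| Section 6.2, general rules and Table 5 | Allows reinstatement after an adverse event and a later increase to the next dose level; Table 5 lists the dose levels | Yes, by permission |
| Section 6.2, first transaminitis event | Allows resumption after grade 2-3, reinitiation after grade 4 with PI consultation, and re-escalation | Yes, by permission |
| Section 6.2, subsequent events in cycles 1-4 | Allows idelalisib to be continued at grade 1 | Yes, but only as continuation |
| Section 6.2, cycle 5 onward | Allows resumption at grade 0 | Yes, by permission |
| Table 6, grade 3-4 non-hepatic and non-hematological events | Allows resumption at a lower dose level or, for listed events, the current one | Yes, by permission |
| Nursing page | Gives administration steps and cites Section 5.2.1 for them | Yes; Section 5.2.1 no longer holds those steps |
| Table 1, idelalisib row | Schedule cell is marked as discontinued | No, although the dose cell still shows 150 mg BID |
| Table 1, ofatumumab row | Places the infusion after an idelalisib dose | Yes, through this cell only |

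**Can a patient already off the drug reach a restart permission?** The cycle 5 onward rule has two triggers. One is AST or ALT above 10 times the upper limit. The other is a rise that goes on after study drug has been stopped. The second can describe a patient withdrawn on 3/11/16, and the rule ends at "LFTs must be checked twice per week until resolution to grade 0, at which time Idelalisib may be resumed". Section 2.5 reports two earlier patients in this trial whose enzymes kept rising after the drug was stopped, so this clinical course has been seen here.

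**Does anything switch the text off?** Section 1.1 shows how that can be done: it describes the planned design, then adds a dated paragraph saying that idelalisib is being discontinued. Section 6.2, Table 6 and the nursing page contain no such statement.

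**The rule that both drugs are held together.** Section 6.1 says that holding one study drug means holding the other. The note under Table 6 says that ofatumumab is held whenever idelalisib is. Section 5 lets patients off idelalisib complete or begin ofatumumab. If a permanent stop counts as a hold, these statements cannot all be followed. The documents do not say whether it does.

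**Reach.** Section 14.1 gives 27 patients at the close of enrollment. That is the ceiling. The documents do not report how many patients were on an idelalisib hold on 3/11/16, or whether anyone received the drug afterwards.

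**The case against.** The best reply is that the controlling text is clear and repeated. Sections 2.5, 5 and 5.2.1 are unqualified, enrollment is closed, and Section 5 cites Section 6 for ofatumumab dose modifications only. Most of the wording in Section 6.2 and Table 6 permits rather than instructs, and restart after a grade 4 event needs consultation with the PI. The nursing page points to Section 5 and Table 1, where a reader would find the stop. It also tells staff to check an alert page that is not in the available copy and might announce it. On this view the fault is incomplete editing.

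Much of that stands. It lowers the chance of actual re-exposure, and it means that Table 1 should not be read as telling staff to give idelalisib. It does not remove the contradiction. A permission to restart is still current text, and the hepatic subsection is addressed to patients who have just stopped.

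Three stronger readings are tempting and unsupported.
- A reader might infer that patients on a hepatic hold at the stop have a route back to the drug. No section says that any such patient existed.
- A reader might use the mortality figures in Section 2.2.4 (7.4% of 664 against 3.5% of 402; 7.4 / 3.5 = 2.1) as the size of this risk. They come from three other trials with different combinations, two of them in previously treated indolent lymphoma, where prophylaxis was not mandated. Section 5.3.6 requires it here. The figures explain the stop and do not measure the effect of leftover wording.
- A reader might infer that ORR and PFS are affected. That would need re-exposure, which is not documented.

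**Conclusion.** The concern holds as an internal contradiction with safety relevance. Section 6.2 and Table 6 permit idelalisib to be continued, restarted or re-escalated, and the nursing page describes giving it, in a protocol that says it will not be given. Table 1 is a minor conflict confined to the ofatumumab route cell. The hold-both-drugs statements conflict with Section 5 only if a permanent stop is read as a hold.

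The reach is unknown and bounded above by 27 patients. The conclusion assumes that Section 6.2, the tables and the nursing page are current operative text, which is how they are presented, and that no page missing from the available copy marks them inactive. It does not assume that anyone was re-exposed.

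**What to change.** The sponsor should reconcile the following with the 3/14/16 amendment and Section 5.2.1:
- Section 6.2, including Table 5, and Table 6;
- the ofatumumab route cell and the idelalisib dose cell of Table 1;
- the hold-both-drugs statements in Section 6.1 and under Table 6;
- the idelalisib entry on the nursing page, including its references to Section 5.2.1.

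Each place should say whether its idelalisib text is still in force. The hold-both-drugs statements should say whether they apply to a permanent stop. The corrected pages should then be reissued to all sites. Which clinical rules apply is for the sponsor to decide; no dose or management rule is proposed here.

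The cost is a wording amendment and redistribution of the pages. It needs no additional data, samples or patients.
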